1.5.3 Potential Benefits

Although the interventional component of the study (randomized biomarker stratified trial of 1 Hz or 10 Hz rTMS and extension trial of cTBS or iTBS for nonresponders) is considered more than minimal risk to adolescents, TMS treatments offer a potential direct benefit for the individual participant.^{33 81,82} Notably all depressed, adolescent participants will received an active form of TMS. There is no placebo or sham condition. In addition, the schedule of mood assessments and daily assessments during the interventional portion of the study for any adverse events has been developed to optimize monitoring the participant's well-being.

Standard TMS dosing (1 Hz and 10 Hz) has been applied more broadly than TBS to children and adolescents in the course of investigational, therapeutic studies.⁸³ The intent for the proposed intermittent theta-burst stimulation (iTBS) and continuous theta-burst (cTBS) exploratory extension trial (Phase II of the proposed study) is to maximize the infrastructure of the proposal for both research participants and our field. Theta burst stimulation (TBS) is an alternative dosing approach in which 3-pulse 50 Hz bursts are delivered at 5 Hz. With iTBS, 2 second trains are delivered to the LDLPFC every 10 seconds for 1800 pulses putatively inducing plasticity changes that resemble long-term potentiation. Continuous theta-burst stimulation (cTBS) delivers 2 second trains of 5 Hz stimulation continuously for 1800 pulses In general it has been speculated that iTBS sessions increase cortical excitability and that cTBS sessions decrease cortical excitability.⁸³⁻⁸⁵

In the course of a NIMH career development award focused on neurostimulation the PI/sponsor has taken every opportunity to interact with national and international clinical communities that focus on the delivery of TMS therapies. This has included volunteering for the Clinical TMS Society Board of Directors, attending International Brain Stimulation conferences, and visiting multiple national and international TMS clinics and laboratories. From these experiences it is clear that TBS protocols are increasingly delivered in clinical settings to adults and adolescents despite a relatively underdeveloped understanding of the in vivo neurophysiological effects in humans. This is particularly concerning in the context of developing children. Systematic study and data collection (efficacy measures, safety, adverse events, and neurophysiological data) focused on TBS is critical in this context. Based on prior experience of the PI, research participants (and their parents) who do not receive benefit from the proposed, primary, experimental therapeutic protocol (Phase I: 6 weeks of either 1 Hz or 10 Hz rTMS) would appreciate the availability of an additional treatment protocol with an experienced center in which safety is maximized. Practically, an extension trial of TBS would also present an

opportunity to maximize resources and collect novel pilot data for future grant submissions (Exploratory Clinical Trials of Novel Interventions for Mental Disorders R61/R33).⁸

1.6 Anticipated Duration of the Clinical Investigation

It is anticipated that the proposed study will be five years in duration. For individual participants, Phase I (biomarker stratified, randomized trial of 1 Hz vs. 10 Hz rTMS) is 10 weeks in duration. Phase II (trial of cTBS vs iTBS based on ICF biomarker status) is 3 weeks in duration.

2 Study Objectives

The proposed study is a dose finding, effectiveness, and target validation study of rTMS for adolescent depression with a biomarker stratified design.⁷² Intracortical facilitation (ICF),⁶⁵ a transcranial magnetic stimulation (TMS) measure of cortical glutamatergic tone is the target engagement biomarker for the proposed trial. In phase I, a cohort of adolescents (ages 12-18) with clinically significant depression defined as 40 or greater on the Children's Depression Rating Scale-Revised (CDRS-R) will be stratified according to baseline ICF (high defined as > 1.5 or low defined ≤ 1.5) and then randomized to 6 weeks of either left prefrontal 1 Hz or 10 Hz rTMS. The research team will collect weekly ICF and CDRS-R measures during treatment. We will assess baseline anhedonia with a composite measure from relevant CDRS-R and Beck Depression Inventory-II (BDI-II) items. We will assess lifetime adversity with the Childhood Trauma Questionnaire (CTQ).

Participants in Phase I will be offered the opportunity to have 3 and 7 T MRI and MRS looking for biomarkers at baseline and after 6 weeks of treatment. A subgroup of depressed adolescent participants (up to 50) who do not respond to 1 Hz or 10 Hz rTMS will be offered the opportunity to participate in an exploratory, 2 week, trial of iTBS or cTBS based on ICF biomarker status (Phase II of the study). Participants with high baseline ICF (defined as > 1.5) will be assigned to cTBS treatment. Participants with low ICF (defined ≤ 1.5) will be assigned to iTBS.

7 T MRS measures Glutamate and GABA biomarkers in healthy adolescents and depressed adolescents. The overall goals are to examine cortical Glutamate and GABA neurochemical markers in adolescent depression and the impact of 1 Hz and 10 Hz rTMS on cortical glutamate and GABA neurochemical markers when compared to the healthy adolescent cohort.

2.1 Primary Objective

Aim 1 examines the relative efficacy of 6 weeks low frequency (1 Hz) or high frequency (10 Hz) left prefrontal rTMS according to a baseline ICF (**ICF-15 % MEP amp**) measure of glutamatergic tone in depressed adolescents. We will employ a biomarker stratified design. Depressed adolescents will be stratified by baseline ICF low (≤ 1.5) or ICF high (>1.5) groups prior to randomization.

- We expect that 6 weeks of 1 Hz rTMS will have greater efficacy (assessed by improvement in CDRS-R) in depressed adolescents with high baseline ICF compared to adolescents with low baseline ICF.
- We expect that 6 weeks of 10 Hz rTMS will have greater efficacy (assessed by improvement in CDRS-R) in depressed adolescents with low baseline ICF compared to adolescents with high baseline ICF.
- 6 weeks of 1 Hz rTMS will have greater efficacy (assessed by improvement in CDRS-R) than 6 weeks of 10 Hz rTMS in depressed adolescents with high baseline ICF.
- 6 weeks of 10 Hz rTMS will have greater efficacy (assessed by improvement in CDRS-R) than 6 weeks of 1 Hz rTMS in adolescents with low baseline ICF.

2.2 Secondary Objective

Aim 2 examines changes in weekly ICF and CDRS-R across 6 weeks of either 1 Hz or 10 Hz rTMS.

- We anticipate that ICF measures will decrease in depressed adolescents receiving 6 weeks of 1 Hz rTMS.
- We anticipate that ICF measures will increase in depressed adolescents receiving 6 weeks of 10 Hz rTMS.

Depressive symptom improvement will have a direct relationship with ICF decrease in depressed adolescents receiving 6 weeks of 1 Hz rTMS and an indirect relationship with ICF increase in depressed adolescents receiving 10 Hz rTMS.

Exploratory Aim 3

Aim 3a: To compare 7 T MRS cortical measures of GABAergic tone and glutamatergic neurochemistry in depressed adolescents and healthy control adolescents.

Aim3b: To examine potential changes in cortical GABAergic and glutamatergic neurochemistry after a six week course of either 1 Hz or 10 Hz rTMS in depressed adolescents.

Hypothesis:

1. Depressed adolescents will have decreased cortical levels of GABA as assessed with 7 T MRS compared to healthy control adolescents.
2. Depressed adolescents will have increased cortical levels of Glutamate as assessed with 7 T MRS compared to healthy control adolescents.
3. Bilateral cortical 7 T MRS measures of GABA will increase after 6 weeks of 1 Hz rTMS in depressed adolescents.
4. Bilateral cortical 7 T MRS measures of Gln/Glu will decrease after 6 weeks of 1 Hz rTMS in depressed adolescents.
5. Bilateral cortical 7 T MRS measures of GABA will decrease after 6 weeks of 10 Hz rTMS in depressed adolescents.

6. Bilateral cortical 7 T MRS measures of Gln/Glu will increase after 6 weeks of 10 Hz rTMS in depressed adolescents.

Exploratory Aim 4 examines clinical moderators of treatment (anhedonia and adversity) in this sample of adolescents undergoing treatment with 1 Hz and 10 Hz rTMS.

Hypothesis:

6 weeks of low frequency (1 Hz) rTMS vs. high frequency (10 Hz) rTMS will have greater efficacy (as assessed by CDRS-R) in depressed adolescents with anhedonia and adversity compared to depressed adolescents without anhedonia and adversity

The proposed project will examine an rTMS dosing, target engagement strategy for adolescent depression and refine understanding of GABAergic and glutamatergic contributions to negative valence. Findings will inform the clinical dissemination of rTMS for adolescent depression and provide insights to further treatment innovation for disorders of the negative valence systems domain early in life.^{9,52}

[figure not shown]
To our knowledge the NeuroStar® TMS Therapy System in XPLORE research configuration has been used most often in prior investigational studies of adolescent depression.^{33,69} Our group has existing and ongoing collaborations with Neuronetics as documented in referenced IDE applications: G060269, G110091, G120121. The present, proposed IDE application would deliver investigational, therapeutic TMS therapy (1 Hz, 10 Hz, cTBS, and iTBS) with the NeuroStar® TMS Therapy System in XPLORE research configuration.

Although the interventional component of the study (randomized biomarker stratified trial of 1 Hz or 10 Hz rTMS and extension trial of cTBS or iTBS) is considered more than minimal risk to adolescents, TMS treatments offer a potential direct benefit for the individual participants.^{33,47} Notably all depressed, adolescent participants will receive an active form of TMS. There is no placebo or sham condition. In addition, the schedule of mood assessments and daily assessments during the interventional portion of the study for any adverse events has been developed for the purpose of monitoring the participants' well-being.

All families and participants for this study will be provided with a consent/assent form describing this study and providing sufficient information for Participants to make an informed decision about their participation in this study. This consent/assent form will be submitted with the protocol for review and approval by the Mayo Clinic IRB. The formal consent/assent of a participant, using the approved IRB consent/assent form, must be obtained before that participant undergoes any study procedure. This form must be signed and dated by the participant the participant's legally-authorized representative, and the individual obtaining informed consent/assent.

3 Study Design

3.1 General Design

Phase I will enroll a cohort (N=120) of adolescents (ages 12-18) with clinically significant depression defined as 40 or greater on the Children’s Depression Rating Scale-Revised (CDRS-R). Participants will be stratified according to baseline ICF (high defined as > 1.5 or low defined ≤ 1.5) and then randomized to 6 weeks of either left prefrontal 1 Hz or 10 Hz rTMS. The research team will collect weekly ICF and CDRS-R measures during treatment. We will assess baseline anhedonia with a composite measure from relevant CDRS-R and Beck Depression Inventory-II (BDI-II) items. We will assess lifetime adversity with the Childhood Trauma Questionnaire (CTQ). Participants will have baseline neurocognitive testing. Participants will have a six month follow-up visit with depression severity measures (CDRS-R and BDI-II) and neurocognitive assessments.

Up to 100 Depressed adolescents will be offered the opportunity to undergo magnetic resonance spectroscopy (MRS) measure at baseline (prior to any Phase I TMS treatment) and posttreatment visits (within 2 months after 6 weeks of TMS treatment in Phase I). A comparison group of 30 healthy control adolescents will be offered the opportunity to undergo MRS at one time point. A subset of up to 50 depressed adolescents who do not respond to Phase I TMS treatment will be offered the opportunity to continue in Phase II (within 2 months of completion of Phase I treatment) for two weeks of either iTBS if (ICF ≤ 1.5) or cTBS if (ICF is >1.5).

Magnetic Resonance Imaging: Depressed and control participants will undergo 3 T structural MRI and ultra-high field (7 T) MRS (7-T, 90-cm horizontal bore magnet interfaced with a Siemens console) to examine GABA, glutamate, and glutamine concentrations in the occipital cortex (OCC). [name] is a co-investigator on this grant and will supervise the collection and analyses of all MRI/MRS data at the Center for Magnetic Resonance Research (CMRR) at the University of Minnesota. Please note that travel time from Mayo Clinic Rochester to the CMRR is approximately 1 hour. Participants will be remunerated for travel and all study visits.

Recent work in adult humans with 7 T MRS and short echo time sequences has enhanced the detection and resolution of GABA, glutamate and glutamine. Spectra will be acquired from a voxel placed in the OCC using the STEAM sequence. Voxels will be prescribed using anatomical landmarks from T1-weighted images. Spectra will be stored separately for subsequent automatic frequency and phase correction (in-house written Matlab routines) using the NAA signal at 2.01 ppm. Summed spectra will be analyzed using LCModel 6.1-4A (Stephen Provencher Inc., Oakville, ON, Canada) and simulated basis sets with a metabolite-nulled macromolecule spectrum measured in vivo. No baseline correction, zero-filling or apodization functions will be applied to the in vivo data prior to the analysis. LCModel fitting will be performed over the spectral range from 0.5 to 4.2 ppm. The quantification will be performed using the unsuppressed water signal obtained from the same voxel. Concentrations will be corrected for cerebrospinal fluid content (the tissue composition will be obtained via voxel segmentation using T1-weighted images acquired at 3 T).

The first MRS will take place following the screening visit but before the baseline/treatment visit occurs. Therefore, a 7 day window is the allowed timeframe for the first MRI and MRS scan. The second MRS will take place within 2 months of completing all rTMS phase I treatments and assessments and before beginning Phase 2 treatments. Screening will include University of Minnesota Center for Magnetic Resonance Research systematic safety assessments for safety to undergo both rTMS and ultra-high field (7 T) MRI/MRS.

Please note that travel time from Mayo Clinic Rochester to the CMRR is approximately 1 hour. Participants will be remunerated \$100.00 per scan for their time and travel expenses.

Research participants: We will enroll participants ages 12 to 18 with the capacity to provide informed assent and parents (for participants younger than age 18) with the capacity to provide informed consent. Capacity to consent will be assessed with comprehension assessments. We are budgeted to recruit 120 depressed adolescents over five years for a target of 100 evaluable subjects (120 accounts for attrition based on our prior experience). We are budgeted to recruit 30 healthy adolescent participants for MRS comparison and test-retest studies. These goals are realistic given our group's experience with therapeutic rTMS and biomarker studies. Screening will include systematic safety assessments for safety to undergo both rTMS and ultra-high field (7 T) MRI/MRS.

Participants who fail to receive clinical benefit from Phase I (defined as a CDRS-R score of 40 or greater at post-treatment) will be offered enrollment in Phase II (N=50 max). The decision to enroll in Phase II can be made by the subject no more than 2 months after the last day of Taper Week 3. During phase II, participants will be assigned to 2 weeks of cTBS if their intracortical facilitation measure (baseline assessment for TBS extension trial) is >1.5 (building on the current speculation that cTBS would be expected to decrease cortical excitability and ICF measures). Participants will be assigned to 2 weeks of iTBS if their ICF (baseline assessment for TBS extension trial) is ≤ 1.5 (building on current speculation that iTBS would increase cortical excitability and ICF measures). All participants in Phase II will have a six month follow-up visit with depression severity measures (CDRS-R and BDI-II) and neurocognitive assessments.

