| Pre/Post Treatment Expectations and Experience Questionnaire (Adolescent and Parent) | Assesses adolescent and parent blinding to treatment arm (1 Hz or 10 Hz) and expectations for treatment outcome. Collected at baseline and posttreatment. |
| SHAPS-Snaith-Hamilton Pleasure Scale | This is a 14 item, self-report measure of validated measure of hedonic capacity. Collected at baseline. |

| Assessment | Description |
|---|--|
| Pediatric Adverse Event Rating Scale | This is a 51 item; self-report measure collected at baseline, weekly during rTMS treatments, posttreatment, and at 6 month follows up visit for adverse event monitoring. |
| Physical Symptoms Checklist | This is a 46 item measure to be collected by the study team (under the supervision of the PI) at baseline, weekly during rTMS treatments, posttreatment, and at 6 month follow up visit for adverse event monitoring. |
| SIT-R3 – Slosson Intelligence Test – Revised | A rapid, validated index of intellectual ability. Its items cover six cognitive domains: Information, Comprehension, Quantitative, Similarities and Differences, Vocabulary, and Auditory Memory. Collected at baseline, if PI the determines there are concerns about cognitive functioning. |
| TASS – Transcranial Magnetic Stimulation Safety Screen | This safety screen is completed prior to TMS for confirmation patient safety. Collected at baseline. |
| UCSD Brief Assessment of Capacity to Consent (UBACC) | This will be given to patients that are 18 years of age who are interested in participating in the MRI/MRS scans at CMRR of age during informed consent. This assesses the patient’s understanding of the MRI/MRS portion of the study. |
| Vital Signs | (Pulse, blood pressure, height, and weight) will be collected at baseline, upon completion of 6 week rTMS (1 Hz or 10 Hz) once again (if applicable) after two week open extension trial (of either cTBS or iTBS), and at 6 month follow up visit. |
| YMRS-Young Mania Rating Scale | This is an 11 item measure used to assess for manic symptoms. The YMRS scale will be completed at baseline and repeated during the course of study participation if symptoms of mania occur in a study participant. If the YMRS is positive, A MINI/MINI-Kid will be repeated to evaluate for mania. If the study participant meets full DSM-5 criteria for mania or hypomania he or she will be discontinued from the study and followed clinically. |

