7.1 Sample Size Determination

Sample Size Estimation and Power Analysis for the Primary Aim of the Study

Using a putative estimate of effect size ($d \sim 0.61$) as it relates to the Primary Aim, an *a priori* sample size estimation and power analysis was performed for the repeated measures design in the proposed study. The results suggest that a sample size of 25 participants per group ($N=120$) achieves 80% power, at a 0.05 alpha level (two-tailed), to detect standardized group mean differences (Cohen's d) as small as 0.61 in a 2-treatment by 2-biomarker status between-Participants group design with 6 (within-Participants) repeated measurements of the primary outcome (depression severity) having a compound symmetry covariance structure, when the assumed within-Participant correlation between observations (depression severity) on the same Participant is ≤ 0.50 (0.50 was based on guidance from our preliminary rTMS work). We anticipate some dropouts (~20% based on treatment discontinuation results from our previous rTMS studies). Thus, ~120 participants will be enrolled to allow for this expected rate of attrition with the intent of capturing a range of evaluable data for 100 participants. The Power Analysis and Sample Size (PASS) 2016 software, version 14.0.7, was used to carry out the sample size and power analysis.⁸⁹

We recognize that to definitively evaluate the relationship between rTMS Treatment (low frequency 1 Hz rTMS vs. high frequency 10 Hz rTMS) by biomarker status (high baseline ICF vs. low baseline ICF) on depression severity—since this relationship has not been previously studied, we have no previous findings to guide effect size selection for the present effort, and the current study would be the first of its kind to examine this effect in depressed youth—we will possibly need a larger sample size than the 100 participants put forth in this proposal. The selection of 100 participants was, in part, resource-driven. The sample size is designed, in part, to detect a moderate effect and to establish a *proof of concept* so as to expand to a subsequent, larger-scale multi-center study. Nevertheless, the current proposal will permit an evaluation of whether receiving low frequency (1 Hz) rTMS vs. high frequency (10 Hz) rTMS treatment according to patients' baseline biomarker status (ICF) shows initial evidence of a relationship with improvement in depression severity in a depressed adolescent population.

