7.2 Statistical Methods

Statistical Methods

All statistical analyses will be carried out using SAS software, version 9.4. The level of significance will be set at $\alpha = .05$ (two-tailed) and, to address multiple testing (where applicable), p-values will be adjusted using the False Discovery Rate.

Primary Aim

Data Analysis Plan for Primary Aim 1 (Hypotheses 1a–1d)

Primary Continuous Outcome: CDRS-R Total Score

Depression severity (measured by CDRS-R total) over the 6-week study period will be the primary continuous outcome measure. A linear mixed model analysis of repeated measures will be used to evaluate the rTMS Treatment (low frequency 1 Hz rTMS vs. high frequency 10 Hz rTMS) by biomarker status (high baseline ICF vs. low baseline ICF) interaction effect on depression severity (CDRS-R total) over 6 weeks of rTMS in depressed adolescents. The model will contain fixed effects terms for rTMS treatment, biomarker status, time, rTMS treatment \times biomarker status interaction, and baseline CDRS-R total score as a covariate. We will consider the inclusion of pubertal state and treatment resistance (as defined by Antidepressant Treatment History Form [ATHF] score) during the study period as additional covariates in the mixed model. Restricted maximum likelihood estimation, Type 3 tests of fixed effects, and generalized least squares will be used, with the Kenward-Roger correction applied to the appropriate and best fitting covariance structure. The sandwich (robust covariance matrix) estimator will also be considered. Least squares (LS) means will be estimated as part of the mixed model. Tests of Simple Effects will be examined so as to partition the interaction LS means effects; i.e., simple group main effects of biomarker status at each level of rTMS treatment (Hypotheses 1a, 1b) and simple group main effects of rTMS treatment at each level of biomarker status (Hypotheses 1c, 1d) will be examined. Cohen's *d* and Hedges' *g* will be calculated and interpreted as the effect size estimator for the between-Participants group main effects. A separate linear mixed model repeated measures analysis similar to that described above will also be implemented over 6 weeks of acute rTMS treatment and throughout the 6-month follow-up period. The PROC

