The multiple mediation/moderation path analytic model, as described in Preacher and Hayes will be used to estimate the direct effect as well as the total and specific indirect effects of rTMS treatment on depression severity (at the 6-week endpoint) through each of the potential baseline moderators (anhedonia and adversity) operating in parallel and, via a separate model, in serial, while controlling for any potential demographics/patient characteristics (not designated as mediators/moderators), including pubertal state and treatment resistance (as defined by ATHF score). A test of the indirect effects will be conducted by bootstrapping standard errors and confidence intervals (95% bias-corrected) from 5,000 bootstrap samples. The procedures of the PROCESS computational SAS macro developed by Hayes will be used to implement the path analytic-based multiple mediation/moderation model.

Sensitivity Analysis

In this section we present a brief sensitivity analysis plan to address incomplete response patterns according to a missing not at random mechanism. First, we will follow the outcome-based model framework of for longitudinal data with non-random missingness along with a model-based approach proposed for modeling both the treatment response and the missing data process.⁹⁰ That is, if deemed necessary, we will build longitudinal models for the data which includes a model for the dropout (or missing data) process so as to assess the sensitivity of the results about the dependence between dropout (or missingness) and treatment response. Additionally, if deemed necessary, we will consider implementing the semi-parametric shared parameter model approach as described in Tsonaka et al. (2009) to handle nonmonotonic nonignorable missingness for mixed-effects models. A Pattern-Mixture Model will also be considered (if necessary).⁹⁰ The results from such (non-random dropout/missingness) models will then be compared with the results of the proposed standard methods (dropout or missing at random models) so as to assess the sensitivity of the results to the effect of dropouts (or incomplete response patterns according to a missing not at random mechanism).

8 Safety and Adverse Events

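### Exploratory Aim 4 scores anhedonia from depression-severity items and names no baseline-severity term, so moderation by overall severity could be reported as moderation by anhedonia

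*Combined protocol and SAP*

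**What the plan says.** Sections 1.5.1, 2 and 3.1 all define the moderator in the same way: "We will assess baseline anhedonia with a composite measure from relevant CDRS-R and Beck Depression Inventory-II (BDI-II) items". They name no items and give no scoring rule. Section 3.1 refers to both scales as measures of depression severity.

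Table 2 describes the SHAPS: "This is a 14 item, self-report measure of validated measure of hedonic capacity. Collected at baseline". Table 3 schedules it at the baseline visit. Section 7 does not mention it.

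Section 2.2 frames the aim as one of moderation: "Exploratory Aim 4 examines clinical moderators of treatment (anhedonia and adversity"). The hypothesis is that the relative efficacy of 1 Hz and 10 Hz on the CDRS-R differs with anhedonia and adversity.

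Section 7.2 specifies a path-analytic mediation/moderation model for treatment effects on "depression severity (at the 6-week endpoint) through each of the potential baseline moderators (anhedonia and adversity"). It is fitted "while controlling for any potential demographics/patient characteristics (not designated as mediators/moderators), including pubertal state and treatment resistance (as defined by ATHF score"). Baseline CDRS-R is not named. The Aim 1 model in the same section does name it: "and baseline CDRS-R total score as a covariate".

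**The concern.** A few items drawn from severity scales will partly measure how depressed the participant is. The Background (section 1.1) itself cites work in which anhedonia in depressed adolescents was associated with illness severity. Suppose the 1 Hz versus 10 Hz difference depends on severity and not on anhedonia as such. A treatment x composite term would then pick up part of that dependence, and nothing named in the Aim 4 model would reveal it.

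The protocol uses anhedonia to argue for targeted treatment, so the interpretation of Aim 4 depends on telling the two apart. The variables that would help are already collected but have no place in the analysis.

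**Working it through.** **The plan's own figure.** The documents give no power or error figure for Aim 4. Section 7.1 gives 25 per group for the primary aim. With d = 0.61, six measures and correlation 0.50, the SD of the mean is sqrt((1 + 5 x 0.5)/6) = 0.764. That returns 25 per group with 80.6% power (normal) or 79.8% (t, 96 df), so the figure reproduces. It is used here only for N = 4 x 25 = 100.

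**How closely could the composite track severity?** Assume 17 equal-variance CDRS-R items (the count is in Table 2) with inter-item correlation c, and a composite of k of them. The correlation with the total is k(1 + 16c) / sqrt(k(1 + (k-1)c) x 17(1 + 16c)).

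- k = 1, c = 0.15: 3.4/sqrt(57.8) = 0.45
- k = 3, c = 0.25: 15/sqrt(382.5) = 0.77
- k = 3, c = 0.35: 19.8/sqrt(572.2) = 0.83

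This is probably high for the trial. Entry requires CDRS-R of at least 40 at screening and baseline (section 4.1), which narrows the range of severity. If the cut falls at the 30th to 70th percentile (assumed), 0.77 drops to 0.64-0.52. BDI-II items, which are not part of the CDRS-R total, change the overlap further. A range of 0.3 to 0.85 is therefore carried forward.

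**What would a treatment x composite test show if only severity moderated?** Let T = ±0.5, severity S and composite A be standardised with correlation r, and outcome = 0.5S + gTS + error with variance s². Here g is the assumed severity slope. With no severity term in the model:

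- expected coefficient on T x A = r x g
- V = s² + (0.25 + g²/4)(1 - r²)
- SE = sqrt(V/(N/4)) = sqrt(V/25)
- z = r x g / SE
- rejection = Φ(z - 1.96) + Φ(-z - 1.96)

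| g | r | s² | V | SE | r x g | z | Rejection, formula | Rejection, simulated |
|---|---|---|---|---|---|---|---|---|
| 0.1 | 0.30 | 1 | 1.230 | 0.222 | 0.030 | 0.14 | 5% | – |
| 0.1 | 0.75 | 1 | 1.110 | 0.211 | 0.075 | 0.36 | 6% | 6% |
| 0.25 | 0.75 | 1 | 1.116 | 0.211 | 0.188 | 0.89 | 14% | 14% |
| 0.5 | 0.75 | 1 | 1.137 | 0.213 | 0.375 | 1.76 | 42% | 40% |
| 0.5 | 0.85 | 1 | 1.087 | 0.208 | 0.425 | 2.04 | 53% | – |
| 0.5 | 0.30 | 0.75 | 1.034 | 0.203 | 0.150 | 0.74 | 11% | 10% |
| 0.5 | 0.85 | 0.75 | 0.837 | 0.183 | 0.425 | 2.32 | 64% | 61% |

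With g = 0 the simulated rate is 5-6% at every r.

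**What each added term does** (simulated at g = 0.5, s² = 0.75, r from 0.3 to 0.85):

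- No severity term: 10% to 61%.
- Baseline severity as a main effect: 12% to 65%. This does not remove the misattribution. Its benefit is precision: the interaction SE falls from 0.216 to 0.207 (r = 0.75, s² = 1).
- Treatment x severity as well: 4% to 5%, the nominal level.

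**What the treatment x severity term costs.** At r = 0.75 and s² = 1 the interaction SE becomes about sqrt(1/(25 x 0.4375)) = 0.30 (0.31 simulated), against 0.21-0.22 without it. If anhedonia truly moderates with slope 0.5, power falls from 63% to 37% at r = 0.75, and from 66% to 24% at r = 0.85.

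**The case against.** A reader might infer that the plan as written would report severity moderation as anhedonia moderation in about half of trials. The documents do not support that, for three reasons.

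- **The test is not written out.** Section 7.2 describes direct and indirect effects of treatment through baseline variables and states no treatment x anhedonia term. Randomised treatment cannot change a baseline score, so such a path is null in expectation whichever instrument is used. The rates above belong to the interaction test that the section 2.2 hypothesis needs, and the mediation/moderation label may or may not include it. This objection stands: the word is could, not would.
- **Sharing items with the outcome scale is not enough.** If severity does not moderate, the test keeps its nominal level. The documents neither state nor hypothesise that severity moderates the 1 Hz versus 10 Hz difference. This also stands.
- **The high rates need a strong slope.** At 0.5 SD per SD, the treatment difference shifts by 2 x 0.5 = 1 SD between participants at -1 and +1 SD of severity, in a trial sized for d = 0.61. At 0.25 and r = 0.75 the rate is 14%.

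A reader might also infer that the SHAPS should replace the composite. That does not follow. The composite combines a clinician rating that takes parent input with self-report, and is a defensible choice. The SHAPS is self-report only and may itself correlate with severity; at a correlation of 0.5 with severity and slope 0.5 it would still reject in about 20-25% of trials.

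Finally, the covariate clause in section 7.2 is open and could admit baseline CDRS-R. A main effect alone would not separate the two explanations, so that does not answer the point. Aim 4 is exploratory, which limits the consequence but does not remove the ambiguity.

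**Conclusion.** The concern holds in a conditional form. Anhedonia is scored from severity-scale items, no baseline-severity term is named for Aim 4, and the SHAPS is collected without a planned use. A positive Aim 4 finding could therefore reflect overall severity, and the plan as written has no analysis to tell.

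The size is unknown. The range of about 5% to 50-60% rests on N = 100, assumed severity slopes of 0.1-0.5, assumed correlations of 0.3-0.85, and an interaction test that the plan implies but does not write out. It should not be quoted as the plan's error rate. Aims 1 and 2 and the sample size are not affected.

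**What to change.** In section 7.2, Aim 4:

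1. Add baseline CDRS-R total as a covariate, as in Aim 1. This uses data already collected and slightly improves precision.
2. Keep the CDRS-R/BDI-II composite as the planned moderator, and write out the treatment x anhedonia term.
3. Prespecify two sensitivity analyses: (a) SHAPS total in place of the composite; (b) treatment x baseline CDRS-R total beside treatment x anhedonia.
4. Make an anhedonia-specific claim only if the result is consistent across these analyses.

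The cost is SAP wording; no new data are needed. Analysis (b) is much less precise because the two interactions are collinear, so a non-significant result there is weak evidence against anhedonia. Direction and size of the estimate should be read along with the p-value. Analysis (a) shares the severity problem to whatever extent the SHAPS tracks severity. For these reasons both belong in sensitivity analyses and not in the main model.
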